1 INTRODUCTION

Why?

We would like to perform an analysis of the relationship between systemic pH and cardiac function and clinical outcome in critically ill patients in patients hospitalized the Intensive Care Unit.

How is it of relevance and importance to patients and public?

Studying this subject we could provide important information about the impact of systemic pH on cardiac function and clinical outcome in seriously ill patients and enable the clinician to

Full title of the research: **The impact of systemic pH on cardiac function and clinical outcome in the critically ill patient.**

IRAS Project ID: **227870**

understand the best treatment of these patients. Patients will be studied who had cardiac monitoring during their ICU admission and an acid-base metabolic disorder. We exclude those patients with cardiac history or who presented an acute coronary syndrome during ICU admission.

IT IS NOT A THERAPEUTIC STUDY. ONLY OBSERVATIONAL. NO INTERVENTIONS.

Where?

In seven different ICU's between King's College NHS Foundation Hospital and Lewisham and Greenwich NHS Trust

How?

The study will take approximately six month to collect prospectively data from each unit. The data will be extracted from the medical notes and ICU charts. No active involvement with participants.

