4 STUDY DESIGN

- Study population and groups: those patients on haemodynamic monitoring in ICU (PiCCO monitoring)
- **Calculation of the sample size:**

Taking into account that the primary objective of the study is to analyze the relationship between the quantitative variables: change in pH and change in Cardiac Contractility, assuming an alpha risk of 5% (95% confidence level), a 20% beta risk (power of 80%) and a minimum ratio that has an estimated clinical significance with a correlation coefficient of 1.5, a bilateral estimate of sample size of 346 subjects is obtained. Assuming a 5% loss (17 individuals) during the study a total of 363 cases would be necessary.

- **Statistical methods:**

The description of quantitative variables is carried out with central tendency and dispersion indices, whether based on values (mean and standard deviation) or on ordinations (median and interquartile range) according to whether they meet normality or not, respectively. Its graphic representation is done with Histograms and Cash Diagrams. The description of categorical variables is performed with absolute and relative frequencies in percentages. Its graphic representation is done with bar charts.

Full title of the research: **The impact of systemic pH on cardiac function and clinical outcome in the critically ill patient.**

IRAS Project ID: **227870**

The relationship between categorical variables is analyzed by comparing proportions with the Pearson Chi-square test, provided that there are less than 20% of squares in the contingency table with expected frequencies less than 5. In the case that there is more 20% of squares with expected frequencies less than 5, the Fisher's exact test is used bilaterally.

The magnitude of the effect of the relationship between two binary variables has been analyzed with the Ratios of proportions or Relative Risk and with the Odds Ratio.

The relationship between a binary exposure variable and a quantitative response is analyzed with the Student-Fisher t test for independent samples if the normality condition is met. According to whether or not the equality of variances are met, the Student-Fisher t test is used for independent groups for homogeneous variances or for non-homogeneous variances, respectively. In case of not fulfilling the condition of normality, the comparison of two means is made with the non-parametric Mann-Whitney U test.

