In the multivariate predictive linear regression model, the criterion of statistical significance was used to decide the maintenance or withdrawal of the predictors in each step. They remain in the model if they are significant and are removed from the model if they are not significant.

In the multivariate models of linear regression, the criterion of clinical significance has been used to decide on the maintenance or withdrawal of the predictors in each step. They remain in the model if they produce a change greater than 10% in the coefficient of the predictor of interest (presence of confounding bias) and withdraw if the change is less than 10% (absence of confounding bias).

The conditions of application of the simple or multiple linear regression (linearity, independence, normality and equality of variances) are evaluated by analysing the residuals.

Values of $P < 0.05$ are considered significant. The statistical treatment has been performed the statistical package SPSS, version 18 (SPSS Inc, Chicago, IL, USA).

Full title of the research: **The impact of systemic pH on cardiac function and clinical outcome in the critically ill patient.**

IRAS Project ID: **227870**

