11 DATA HANDLING AND MANAGEMENT

Where data will be recorded: initially on paper with a reference code for each patient. On enrolment the patient is given a unique study ID. This usually has a numeric code for the site as well as a sequential number for patients e.g 23-001, 23-002 etc. the case report forms (data collection forms) only have study ID on. There is no patient ID at all on the CRF, but we have an enrolment log- just a list of name, hospital number and study ID.

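### Patients from seven ICUs are pooled with no planned ICU term or allowance for clustering; the pH slope may be confounded by unit and its standard error may be too small, and fixed ICU indicators would prevent both at almost no cost.

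*Combined protocol and SAP*

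**What the plan says.** Section 1 (Introduction) places the study "In seven different ICU's" across two organisations. The statistical methods appear three times (study summary, section 4 and section 8). Each copy specifies two-sample tests, Pearson or Spearman correlation, and simple or multiple linear regression. The main estimative model regresses change in cardiac output on change in pH, both taken between the lowest and highest pH. Its candidate confounders are not listed, and one is kept only if it moves the pH coefficient by more than 10%.

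No copy mentions ICU, site, stratification, a random effect or a clustered standard error. The one reference to independence is that the regression conditions ("linearity, independence, normality and equality of variances) are evaluated by analysing the residuals"), with no action stated if a condition fails. The sample size in section 4 has no design effect: "a bilateral estimate of sample size of 346 subjects is obtained".

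On identifying the unit, section 11 says of the study ID: "This usually has a numeric code for the site as well as a sequential number for patients". The data form, as far as it is shown under section 20, has ICU admission and discharge dates but no field for which ICU.

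**The concern.** Patients in one ICU share case mix, staff and local habits. Section 16.8 leaves the decision to use PiCCO to the consultant in charge, so entry to the study depends partly on the unit. The exposure is the gap between lowest and highest pH, read from notes and charts with no stated sampling schedule. A range tends to widen with more readings, so a unit that samples more often could show larger pH changes for that reason alone. It is therefore plausible, though not documented, that pH change clusters by unit.

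Two separate problems could follow. If both pH change and response cluster, the pooled regression treats patients as more independent than they are and its standard error may be too small. If units with larger pH changes also tend to have larger or smaller cardiac responses for other reasons, that between-unit pattern enters the pooled slope and may pass for a pH effect. Inspecting residuals repairs neither. The result at stake is the primary association.

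**Working it through.** **Inputs from the documents.** Seven ICUs (section 1); two-sided 5% level, 80% power, N = 346 before loss and 363 after (section 4). The correlation is printed as 1.5 ("estimated clinical significance with a correlation coefficient of 1.5"), which no correlation can be.

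**Assumed inputs.** ICCs of pH change (ICC_x) and of response (ICC_y) from 0 to 0.10; correlation of the two sets of ICU effects from −0.5 to 0.8; equal unit sizes. The documents give none of these. The target of 0.15 is stated for contractility and is carried over here to cardiac output.

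**The plan's own figure.** With Fisher's z, n = ((1.960 + 0.842)/atanh(r))² + 3. At r = 0.15 this gives 346.6, matching 346. At r = 1.5 the formula is undefined, so 0.15 is evidently the value used. For losses, 346 × 1.05 = 363.3, matching 363.

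**Standard error if ICU is ignored.** The exposure varies between patients within a unit, so the design effect depends on both ICCs: DE = 1 + (m − 1) × ICC_x × ICC_y, with m = 346/7 = 49.4. The true standard error is √DE times the reported one, and the actual two-sided error is 2 × (1 − Φ(1.96/√DE)).

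| ICC_x / ICC_y | DE | √DE | Actual error, formula | Simulated |
|---|---|---|---|---|
| 0 / 0.05 or 0.10 | 1.00 | 1.00 | 5.0% | 5.0–5.2% |
| 0.05 / 0.05 | 1.12 | 1.06 | 6.4% | 6.9% |
| 0.05 / 0.10 | 1.24 | 1.11 | 7.9% | – |
| 0.10 / 0.10 | 1.48 | 1.22 | 10.8% | 9.0% |

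For example, 1 + 48.4 × 0.10 × 0.10 = 1.48. The simulation used 7 units of 49 patients, 6,000 runs per scenario, no true within-unit effect and uncorrelated ICU effects.

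**Bias in the pooled slope.** Same simulation, with ICU effects on pH change and response correlated, in SD units:

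| ICCs (both) | Correlation of ICU effects | Bias | Bias / 0.15 |
|---|---|---|---|
| 0.05 or 0.10 | 0 | nil | 0 |
| 0.05 | 0.5 | 0.022 | 0.15 |
| 0.10 | 0.5 | 0.043 | 0.29 |
| 0.10 | 0.8 | 0.069 | 0.46 |
| 0.10 | −0.5 | −0.043 | −0.29 |

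**With ICU indicators.** In every scenario simulated, bias was at most 0.001 SD and the error rate was 4.7% to 5.7%. Power at N = 346 and r = 0.15, from the noncentral t distribution, is 80.4% with 344 residual degrees of freedom (no ICU terms) and 79.7% with 338 (six indicators), a loss of 0.7 points.

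**The case against.** The strongest reply is that none of this is shown to happen. The documents give no ICC. When pH change does not cluster, pooled regression stays valid however strongly the response clusters, and without correlated ICU effects there is no bias. That stands, and it is why the point is worded as a risk.

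The second reply is that the plan may already cover it: candidate confounders are unnamed, and polytomous predictors are entered as indicators, so ICU could be among them. If ICU were offered under the 10% rule, simulation of the estimative model gave an error rate of 5.0% to 5.6% and power within 0.3 points of always keeping it. That stands too. Exempting ICU from the rule therefore gains little in that model; the real gap is that nothing commits the analyst to offering ICU at all. The unadjusted correlation on which the sample size rests cannot take an ICU term in any case.

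Three stronger readings are tempting, and the documents do not support them:

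- A reader might infer that the standard errors are certainly too small and the slope certainly confounded. Both depend on unreported quantities.
- A reader might divide 346 by the design effect and infer a large loss of power. That describes neither analysis. The planned test uses its uncorrected standard error and, with uncorrelated ICU effects, rejects at Φ(0.84/√DE), about 79%, 78% and 76% for design effects of 1.12, 1.24 and 1.48. The model with ICU terms has about 79.7%.
- A reader might infer that every study ID already identifies the ICU. Section 11 says the code is usually present and refers to the site; seven ICUs lie in two organisations, so it may not identify the unit.

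**Conclusion.** The point holds as an omission with conditional consequences. Seven units are pooled, no ICU term or allowance for clustering is planned, and the independence check has no stated consequence. Under assumed ICCs of 0.05 to 0.10 for both variables, the nominal 5% test runs at about 6% to 11% by formula and about 7% to 9% simulated. With positively correlated ICU effects (0.5 to 0.8), bias is about 0.02 to 0.07 SD, or 15% to 46% of the 0.15 target; a negative correlation reverses its sign. If pH change does not cluster by ICU, both problems disappear. These figures rest on assumed ICCs, equal unit sizes and a target of 0.15 in place of the printed 1.5. The risk cannot be sized from the documents, but it touches the primary analysis and is cheap to remove, so the change should be made.

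**What to change.** In all three copies of the statistical methods:

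1. Prespecify ICU as a fixed factor (six indicators) in the estimative regression of change in cardiac output on change in pH, kept whatever the 10% rule gives.
2. Name that ICU-adjusted slope as the primary result, in place of the unadjusted correlation.
3. Include ICU in any regression later specified for mortality. None is specified now.
4. Add a field for the ICU to the data form. Screening is done daily in each ICU (section 7, Recruitment), so the unit is known at enrolment.

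Fixed indicators are preferable to ordinary cluster-robust standard errors, which are unreliable with only seven clusters and would leave between-unit confounding in place. The plan already codes polytomous predictors as indicators, so no new method is needed.

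The cost is revised wording, six degrees of freedom (power about 80.4% to 79.7%) and one extra field per patient. The printed correlation of 1.5 also needs correcting to the value used; that is a separate point.

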2 BACKGROUND AND RATIONALE

3 OBJECTIVES

Goals

Primary

1. Assess whether there are significant changes in cardiac function associated with changes in blood pH.
2. Relate the changes in cardiac function to presence or absence of underlying cardiac disease.

Secondary

3. To establish which factors affected by blood pH have an impact on cardiac function.

Full title of the research: **The impact of systemic pH on cardiac function and clinical outcome in the critically ill patient.**

IRAS Project ID: **227870**

4. Study the mortality of patients admitted to the Intensive Care Unit (ICU) who had continuous cardiac monitoring at any time during their admission and relate it to changes in blood pH.

4 STUDY DESIGN

- Study population and groups: those patients on haemodynamic monitoring in ICU (PiCCO monitoring)
- **Calculation of the sample size:**

Taking into account that the primary objective of the study is to analyze the relationship between the quantitative variables: change in pH and change in Cardiac Contractility, assuming an alpha risk of 5% (95% confidence level), a 20% beta risk (power of 80%) and a minimum ratio that has an estimated clinical significance with a correlation coefficient of 1.5, a bilateral estimate of sample size of 346 subjects is obtained. Assuming a 5% loss (17 individuals) during the study a total of 363 cases would be necessary.

- **Statistical methods:**

The description of quantitative variables is carried out with central tendency and dispersion indices, whether based on values (mean and standard deviation) or on ordinations (median and interquartile range) according to whether they meet normality or not, respectively. Its graphic representation is done with Histograms and Cash Diagrams. The description of categorical variables is performed with absolute and relative frequencies in percentages. Its graphic representation is done with bar charts.

Full title of the research: **The impact of systemic pH on cardiac function and clinical outcome in the critically ill patient.**

IRAS Project ID: **227870**

The relationship between categorical variables is analyzed by comparing proportions with the Pearson Chi-square test, provided that there are less than 20% of squares in the contingency table with expected frequencies less than 5. In the case that there is more 20% of squares with expected frequencies less than 5, the Fisher's exact test is used bilaterally.

The magnitude of the effect of the relationship between two binary variables has been analyzed with the Ratios of proportions or Relative Risk and with the Odds Ratio.

The relationship between a binary exposure variable and a quantitative response is analyzed with the Student-Fisher t test for independent samples if the normality condition is met. According to whether or not the equality of variances are met, the Student-Fisher t test is used for independent groups for homogeneous variances or for non-homogeneous variances, respectively. In case of not fulfilling the condition of normality, the comparison of two means is made with the non-parametric Mann-Whitney U test.

The comparison between a polytomic predictor and a quantitative response is made through the analysis of variance (ANOVA) in the case of meeting the conditions of normality and homogeneity of variances. If any of these conditions is not met, it is done with the non-parametric H test of Kruskal-Wallis. If the polytomic predictor is ordinal, the ANOVA trend test or the non-parametric Jonckheere-Terpstra trend test is also used, depending on whether normality is met or not, respectively.

Full title of the research: **The impact of systemic pH on cardiac function and clinical outcome in the critically ill patient.**

IRAS Project ID: **227870**

The relationship between two independent quantitative variables is evaluated with the correlation coefficient r of Pearson if normality is met, or with the nonparametric correlation coefficient ρ of Spearman if normality is not met. Its graphic representation is made with the scatter diagrams or points.

Normality is assessed with the Kolmogorov-Smirnov test with the Lilliefors significance correction for large samples, or with the Shapiro-Wilks test for small samples. The equality of variances is analyzed with the Levene variance homogeneity test.

The relationship between two related quantitative variables is performed using the Student-Fisher t-test for related samples in case the normality condition is met. Otherwise, the non-parametric Wilcoxon T test is used. The relationship between two paired categorical variables is performed by the McNemar symmetry test.

The relationship between a continuous quantitative response and one or several predictors, whether binary, polytomic or quantitative, is done with Simple or Multiple Linear Regression respectively.

The polytomous predictors variables are introduced in the Linear Regression models broken down into binary indicator variables coded with respect to the first reference category.

An estimative multivariate linear regression model of the effect of the predictor Change of pH (between the lowest and highest pH) on the response Change in cardiac output

Full title of the research: **The impact of systemic pH on cardiac function and clinical outcome in the critically ill patient.**

IRAS Project ID: **227870**

(corresponding to the moments between the lowest and the highest pH) has been performed. The possible role as confounding factors of several variables on this relationship has been evaluated. A predictive multivariate model of linear regression has been performed to evaluate the factors that intervene in the Cardiac Contractility.

Both the predictive and the estimative models have been carried out with the manual backward step procedure using the criterion of decreasing statistical significance to establish the order to evaluate the withdrawal or permanence of each predictor.

In the multivariate predictive linear regression model, the criterion of statistical significance was used to decide the maintenance or withdrawal of the predictors in each step. They remain in the model if they are significant and are removed from the model if they are not significant.

In the multivariate models of linear regression, the criterion of clinical significance has been used to decide on the maintenance or withdrawal of the predictors in each step. They remain in the model if they produce a change greater than 10% in the coefficient of the predictor of interest (presence of confounding bias) and withdraw if the change is less than 10% (absence of confounding bias).

The conditions of application of the simple or multiple linear regression (linearity, independence, normality and equality of variances) are evaluated by analysing the residuals.

Full title of the research: **The impact of systemic pH on cardiac function and clinical outcome in the critically ill patient.**

IRAS Project ID: **227870**

Values of $P < 0.05$ are considered significant. The statistical treatment has been performed the statistical package SPSS, version 18 (SPSS Inc, Chicago, IL, USA).

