	analyze the relationship between the quantitative variables: change in pH and change in Cardiac Contractility, assuming an alpha risk of 5% (95% confidence level), a 20% beta risk (power of 80%) and a minimum ratio that has an estimated clinical significance with a correlation coefficient of 1.5, a bilateral estimate of sample size of 346 subjects is obtained. Assuming a 5% loss (17 individuals) during the study a total of 363 cases would be necessary.
Trial design and methods	It is not a trial
Trial duration per participant:	It is not a trial
Main inclusion/exclusion criteria:	
EXCLUSION CRITERIA
 
 • Atrial or ventricular arrhythmia: you need a stable pulse to measure the contour. • Aortic, mitral or tricuspid valve insufficiency. In the case of valve insufficiency the valve does not close correctly. Therefore, the thermodilution curve is affected by indicator regurgitation, resulting in a prolonged indicator decay time. • Intra-Aortic Balloon pump: once again, the pulse contour is all wrong; but you can still get thermodilution cardiac output measurements. • Aortic aneurysm: the contour will be bizarre because the arterial compliance is going to be weird, with the aortic aneurysm acting as a damping system by absorbing all the pressure wave. • Extracorporeal circuit: when you are on bypass, there is no real arterial waveform • Pneumonectomy: PiCCO relies on there being a relatively normal pulmonary vasculature. • Massive pulmonary embolism: as above; it is essentially a pneumonectomy by embolism. • Intracardiac shunt: the PA catheter will also give an inaccurate thermodilution reading. • Less than a minimal tidal volume 6-

Full title of the research: **The impact of systemic pH on cardiac function and clinical outcome in the critically ill patient.**

IRAS Project ID: **227870**

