	
The relationship between two independent quantitative variables is evaluated with the correlation coefficient r of Pearson if normality is met, or with the nonparametric correlation coefficient ρ of Spearman if normality is not met. Its graphic representation is made with the scatter diagrams or points.
 
Normality is assessed with the Kolmogorov-Smirnov test with the Lilliefors significance correction for large samples, or with the Shapiro-Wilks test for small samples. The equality of variances is analyzed with the Levene variance homogeneity test.
 
The relationship between two related quantitative variables is performed using the Student-Fisher t-test for related samples in case the normality condition is met. Otherwise, the non-parametric Wilcoxon T test is used. The relationship between two paired categorical variables is performed by the McNemar symmetry test.
 
The relationship between a continuous quantitative response and one or several predictors, whether binary, polytomic or quantitative, is done with Simple or Multiple Linear Regression

--	---

Full title of the research: **The impact of systemic pH on cardiac function and clinical outcome in the critically ill patient.**

IRAS Project ID: **227870**

	
respectively.
 
The polytomous predictors variables are introduced in the Linear Regression models broken down into binary indicator variables coded with respect to the first reference category.
 
An estimative multivariate linear regression model of the effect of the predictor Change of pH (between the lowest and highest pH) on the response Change in cardiac output (corresponding to the moments between the lowest and the highest pH) has been performed. The possible role as confounding factors of several variables on this relationship has been evaluated. A predictive multivariate model of linear regression has been performed to evaluate the factors that intervene in the Cardiac Contractility.
 
Both the predictive and the estimative models have been carried out with the manual backward step procedure using the criterion of decreasing statistical significance to establish the order to evaluate the withdrawal or permanence of each predictor.
 
In the multivariate predictive linear regression model, the criterion of statistical significance was used to decide the maintenance or withdrawal of the predictors in each step. They

--	--

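### The primary, powered relationship is pH change versus contractility change, but the only named confounder-adjusted pH model has cardiac output change as its response

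*Combined protocol and SAP*

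**What the plan says.** All references are to the Combined protocol and SAP.

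- **Sample size** (Section 4; same paragraph in the Study summary under Target sample size): "the primary objective of the study is to analyze the relationship between the quantitative variables: change in pH and change in Cardiac Contractility". With a two-sided alpha of 5%, power of 80% and a minimum correlation printed as 1.5, the paragraph arrives at 346 subjects, and at 363 after adding 17 for a 5% loss.
- **Estimative model** (Study summary, Section 4 and Section 8, same text each time): the predictor is the change in pH between its lowest and highest values, and its effect is estimated "on the response Change in cardiac output (corresponding to the moments between the lowest and the highest pH) has been performed". The next sentence adds: "The possible role as confounding factors of several variables on this relationship has been evaluated".
- **Predictive model** (same places): a linear regression of what influences cardiac contractility. It does not describe contractility as a change and does not list pH change as a predictor. Predictors stay only if statistically significant.
- **Goals** (Section 3): primary goal 1 is "Assess whether there are significant changes in cardiac function associated with changes in blood pH". Secondary goal 3 is "To establish which factors affected by blood pH have an impact on cardiac function". Neither names a measure.
- **Hypothesis** (Study summary): the animal evidence is described in terms of cardiac output, and the human hypothesis in terms of cardiac function.
- **Generic rules** (Sections 4 and 8): "The relationship between two independent quantitative variables is evaluated with the correlation coefficient r of Pearson if normality is met", with Spearman otherwise. A separate sentence allows simple or multiple linear regression for any continuous response.

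**The concern.** This is an observational study in intensive care patients, so the estimate that deals with confounding is the one most readers will rely on. The plan assigns that estimate to cardiac output, while naming contractility as the response of the primary objective and sizing the study on it. The two terms are the responses of two different models in adjacent sentences, so the plan does not use them as synonyms.

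What is at stake is which result answers primary goal 1. With two candidate responses, a common P < 0.05 threshold and no stated order between them, the choice could be made after the results are known. A reader of the final report could not tell from the plan whether the adjusted cardiac output slope or some analysis of contractility was meant to be primary.

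**Working it through.** **Step 1. Set the places side by side.**

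| Place | Response named | pH change named? | Adjusted for confounding? |
|---|---|---|---|
| Goal 1 (Section 3) | cardiac function, no measure | changes in blood pH | not stated |
| Hypothesis (Study summary) | cardiac output in the animal evidence; cardiac function in humans | changes in blood pH | not stated |
| Sample size (Study summary, Section 4) | change in contractility | yes | no, a simple correlation |
| Estimative model (Study summary, Sections 4 and 8) | change in cardiac output | yes, as the predictor of interest | yes |
| Predictive model (same places) | contractility, not stated as a change | no | not designed for it; keeps significant predictors |
| Generic Pearson/Spearman rule | none | no | no |
| Generic linear regression rule | none | no | possible, not specified |

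No row joins pH change, change in contractility and confounder adjustment in a named analysis. The 10% change-in-coefficient rule is worded for multivariable linear models in general. It needs a predictor of interest, and only the cardiac output model has one.

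**Step 2. Reproduce the plan's sample size.** Inputs from Section 4: alpha 0.05 two-sided, power 0.80, correlation printed as 1.5. The Fisher z formula is n = ((z for alpha/2 + z for power) / atanh(r))² + 3.

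- With r = 1.5, atanh is undefined, because a correlation cannot exceed 1.
- Assuming 0.15 was meant, atanh(0.15) = 0.15114. Then n = ((1.95996 + 0.84162) / 0.15114)² + 3 = 343.6 + 3 = 346.6, which agrees with the stated 346.
- Loss: 346 × 0.05 = 17.3, taken as 17, and 346 + 17 = 363, as stated.

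**Step 3. See what the 346 supports.**

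- Power at 346 with r = 0.15: 0.15114 × √343 − 1.960 = 0.839, and Φ(0.839) = 79.9%.
- Smallest correlation with 80% power at 346: tanh(2.80158 / √343) = 0.150. This holds for any response, but the plan states its minimum relevant correlation only for contractility.

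**Step 4. Ask what can be said for cardiac output.** The documents give no correlation for it. By the same formula, assumed values of 0.12, 0.15 and 0.20 give power at 346 of 60.8%, 79.9% and 96.4%. The range runs both ways. It shows only that the 80% cannot be carried over without a stated correlation.

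**The case against.** **The powered analysis is in the plan.** The study is sized on a correlation between two quantitative variables, and such pairs are analysed by Pearson or Spearman. Power and test therefore match for contractility, and the plan never claims 80% power for the adjusted model. Sizing on a simple correlation and then adjusting by regression is not in itself an error. All of this stands.

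**Regression of contractility on pH change is allowed.** The generic regression sentence covers it as well as the Pearson sentence covers the unadjusted pair. A reader might infer that the plan leaves the primary relationship with an unadjusted correlation only. The text does not support that. What remains is that an adjusted contractility model is permitted but not specified, while the cardiac output model is.

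**Cardiac output may be the intended response.** The evidence behind the hypothesis is in terms of cardiac output, so contractility in the sample-size paragraph may be the loose term. This is plausible, and it is why the fix leaves the choice to the investigators. It does not remove the discrepancy, because the same paragraph states the primary objective outright.

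**Cardiac function can include both measures.** It can, but that wording does not rank them.

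**Conclusion.** The concern holds as a mismatch of responses that no section reconciles. The primary objective and the sample size concern change in contractility, the only named confounder-adjusted model of pH change concerns change in cardiac output, and no text says which is primary. The documents give no basis for a numerical measure of its effect. The consequence is that the plan does not determine which estimate answers primary goal 1.

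Two stronger readings are not supported. A reader might infer that the study is underpowered for its adjusted analysis. Without a correlation for cardiac output, its power could lie above or below 80%. A reader might also infer that the significance rule in the predictive model will delete the primary estimate. That model is not said to contain pH change, and significance-based selection is a separate question that would remain if the responses agreed.

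The textual finding rests on no numerical assumption. Only the reproduction of 346 does, since it takes the printed 1.5 as 0.15.

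**What to change.** Before analysis, use one primary response in the goals, the sample-size paragraph and the estimative model, and label the other secondary. Either choice resolves the point.

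- **If contractility is primary:** run the estimative model on the change in contractility between the lowest-pH and highest-pH moments. Keep pH change in the model throughout and use the 10% rule to choose confounders. Name the PiCCO variable that represents contractility; the available text does not give it, though the data form printed under Section 20 may be cut short. Keep the cardiac output model as secondary. At an assumed correlation of 0.15 the sample-size basis does not change.
- **If cardiac output is primary,** which fits the evidence in the hypothesis: reword the sample-size paragraph to cardiac output, state and justify its minimum relevant correlation, and restate power at 346 analysed. A minimum below about 0.150 would put power at 346 below 80%; an assumed 0.12, for example, would need 543 analysed. Label contractility secondary.

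The cost is wording in the Study summary and Sections 3, 4 and 8, one variable definition if contractility is chosen, and at most one extra regression. No extra patients are needed if contractility stays primary at 0.15.
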